Study Design: We propose a double-blind placebo controlled proof of concept pilot study of active versus sham LFR rTMS for the treatment of TBI depression. As noted above, all subjects will be screened prior to randomization. During the screening visit, all subjects will undergo a complete psychiatric evaluation as well as formal cognitive testing. In addition, if there is any possibility of pregnancy or unstable medical status, the PI or physician co-investigator will ask the potential subject's treating psychiatrist or primary care physician (PCP) to conduct a urine pregnancy test and/or bloodwork to rule out infections and liver, kidney or thyroid abnormalities. If the potential participant does not have a PCP or psychiatrist, a lab requisition will be provided to the participant. He/she will be considered for the study only after the lab results are reviewed by the study physician and found to be normal. .

Subjects will be randomized using a custom in-house software method, and will be stratified on time since injury: <5 years post injury versus ≥ 5 years.

All members of the research team will be blind to individual subjects' treatment condition, with the exception of the rTMS staff member, [name]. The success of subject blinding will be evaluated by asking subjects, during the first and last week of treatment, whether they believe that they received active or sham rTMS treatment. The rTMS technician will ask this question and note down the answer in the weekly assessment form.

Study Treatment: Subjects will receive either LFR rTMS or sham treatment.

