Although LFR rTMS is often delivered to patients at 120% MT (consistent with FDA approval of HFL rTMS at 120% MT), most studies of LFR rTMS use 110% MT, which would carry a lower seizure risk than 120% MT. Accordingly, we will use 110% MT in our study. Two leading TMS groups studying LFR rTMS as an antidepressant have used 900 pulses daily over 4 weeks⁷⁸ and 1600 pulses daily over 2 weeks⁷⁰ in controlled studies. Both produce similar decreases in HAMD at their respective endpoints. Other sham-controlled studies have demonstrated an antidepressant effect with as few as 300 – 600 pulses daily delivered for 2 – 3 weeks^{69, 74, 89}. Pulses are sometimes delivered in one continuous train^{70,78} and at other times they have been delivered in several trains separated by an intertrain interval (ITI) of 30 – 60 seconds^{69,89,90}, which could reduce seizure risk still further. We propose to deliver 1200 pulses daily at 110% MT for 4 weeks using four trains of 300 pulses daily separated by an ITI of 60 seconds. This parameter set also lies well within TMS safety guidelines most recently updated in Rossi et al⁹¹.

The rTMS treatment sheet will be used after each treatment to record treatment parameters, treatment interruption, if any, and adverse events during treatment. The form has been uploaded in the IRB application under Section 19 – ‘Supplemental Study Documents..

All participants will also receive supportive care. This will include education about TBI and depression and a discussion of the importance of maintaining structure/routine, regular physical exercise, engaging in hobbies and maintaining balanced/regular nutrition. Subjects who become suicidal or develop problems that require aggressive treatment during the course of the study will be withdrawn, and followed at the PI’s Brain Injury Clinic, if appropriate care can be provided on an outpatient basis. If outpatient care is not appropriate, the PI will be responsible for admitting subjects to the psychiatric inpatient units at either Johns Hopkins Bayview Medical Center or Johns Hopkins Hospital.

Justification for use of Placebo:

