The post-TBI depression field is currently at equipoise regarding the efficacy of antidepressant medications vs. placebo. There are no studies that have done a risk-benefit assessment on the use of anti-depressants vs placebo in the treatment of post-TBI depression. As the proposed treatment trial duration is only 16 weeks and all participants will have regular follow-up visits, those receiving sham treatment will not be at a great disadvantage compared to those receiving active LFR rTMS, as they will also receive regular supportive care. There is no evidence in psychiatric research that short-term treatment with placebo produces lasting harm (Addington and Quitkin 1999). However, if during follow-up visits, it is ascertained that a participant’s depression is worsening with development of active suicidal thoughts, the participant will be withdrawn from the study for more active treatment (inpatient admission vs day hospital admission vs. aggressive outpatient treatment with medications). Careful screening of all participants will be done and no one who has responded well to a particular medication in the past will be enrolled in the study. Finally, the study will be carefully discussed with all participants emphasizing the risks and benefits of joining the study. All participants will also be encouraged to talk to their physicians about the pros and cons of joining a placebo-controlled trial.

In summary, the proposed study has the potential to reveal the effectiveness of LFR rTMS over placebo or vice-versa, underscoring the clinical utility and scientific merit of the study.

Justification for use of a two arm study versus a cross-over design study:

A cross-over design has the potential to confound study results, as the effect of rTMS treatments may last considerably longer than the duration of administration, and this prolonged effect is of unpredictable and unmeasurable duration. For this reason, crossover designs are no longer used to assess the efficacy of antidepressants/rTMS in treatment of major depression in general. As such, we do not feel it would be appropriate for assessing the efficacy of LFR rTMS for the treatment of post-TBI depression.

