There is no Food and Drug Administration (FDA) approved drug for the treatment of TBI-related NPS symptoms/syndromes. There are only two controlled medication trials in TBI-associated depression, and neither provided strong evidence that antidepressants are superior to placebo. A major limitation of previous studies has been their focus on limited symptoms and use of agents with narrow therapeutic profiles. We propose to address some of these limitations by use of a novel non-invasive technique, LFR rTMS, that has the potential to induce widespread neuromodulation.

Justification and safety information if FDA approved drugs will be administered for non-FDA approved indications or if doses or routes of administration or participant populations are changed. NA

Justification and safety information if non-FDA approved drugs without an IND will be administered. NA. We anticipate that the Johns Hopkins IRB will classify our trial as significant risk, in which case we will require an IDE from the FDA.

6. Study Statistics

General Description

- a. Definition and selection of dataset: Intention-to-treat (ITT) will include all subjects who are randomized to participate in the protocol. The per-protocol (PP) population will include all subjects in the ITT population who meet the additional criteria of no major protocol violations and compliance with study treatment. Baseline demographic and clinical features, including medical comorbidity, pain, fatigue, and post-concussive symptoms will be included in the ITT dataset. Effect assessment will be included in both the ITT and PP dataset.
- b. Basic exploratory analyses will first be conducted, including checking of distributional assumptions, assessment of relationships among covariates, and missing-value multiple imputations.
- c. Continuous variables will be described using means, standard deviations, medians, minimums and maximums, and 95% confidence intervals for parameter estimation. Graphical display (spaghetti plots) of the outcome scores will also be generated for 5 visits (baseline, end of 20 LFR rTMS sessions, week 8,12, and 16) by group. Category and count variables will be described using frequency or proportions.
- d. Analyses will be conducted using STATA 11.2 (StataCorp, Texas, 2009) or R 2.13.2 (2011). All statistical tests will be judged for significance based upon a two-sided p-value of less than 0.05.

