Primary objective: To determine the effectiveness of LFR rTMS for the symptomatic treatment of: (a) post-TBI depression as assessed by the Hamilton Depression Rating Scale (HAMD), Patient Health Questionnaire 9 (PHQ9) and the Clinical Global Impression-Improvement (CGI-I) scale; and (b) suicidal ideation as assessed by Beck Scale for Suicide Ideation (BSS).

Hypothesis:

- a. Participants in the rTMS group (Experimental group), when compared to the sham treatment group (Control group) will have statistically significantly lower HAMD PHQ 9 scores (improvement in depression) and higher CGI-I scores (global improvement) at the end of the active treatment period (i.e., after 20 sessions) and during the follow-up period (i.e., week 8, 12, and 16 follow-up).
- b. Participants in the rTMS group (Experimental group) compared to the sham treatment group (Control group) will have significantly lower scores on the BSS (less suicidality) at the end of the active treatment period (i.e., after 20 sessions) and during the follow-up period (i.e., week 8, 12, and 16 follow-up).

Data Collection: The PI will be responsible for conducting comprehensive clinical evaluations on all subjects and for maintaining the psychiatric, medical and TBI data. rTMS and sham treatments will be administered by [name], another TMS credentialed psychiatrist or the TMS technician. Data pertaining to treatments will be maintained by the TMS Program Coordinator. Three TMS forms (adverse effects, Weekly assessment & Operator form) have been uploaded for review. Co-investigator, [name] will be responsible for the sleep data and [name] will be responsible for the cognitive data. At the end of the study, the PI and her research coordinator will be responsible for obtaining databases from each of the co-investigators, and merging data into a master database.

Variables and Measures:

Demographic & Clinical Variables: Demographic information including age, gender, education level, vocational status, living situation, annual income and marital status will be collected as part of the baseline evaluation. Other pertinent clinical variables, such as cause of trauma (assault vs. motor vehicle accident),

and litigation status will also be recorded. The VA/DoD definition of severity of TBI will be used to assess severity of TBI.

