Treatment response: The Clinical Global Impression (CGI)^{98,99} scales are used to rate the severity of illness and assess response to treatment. CGI-Severity scale (CGI-S) is used to assess the severity of illness and CGI – Improvement scale (CGI-I) is used to assess treatment response in psychiatric patients. Both are 7-items scale. The CGI-S ranges from 1= normal to 7 = extremely ill.. The CGI-I rates participants improvement from baseline: 1=very much improved; 7=very much worse.

Primary Efficacy Measures: Changes in HAMD, PHQ9 and BSS;

Statistical Analysis

- a. All subjects will be tracked over the study period in order to capture (1) the number subjects randomized to each group; (2) the number of subjects who drop-out or are lost to follow-up, and (3) the compliance of each subject across the study period.
- b. Baseline balance analyses: At baseline, the two groups (Experimental and Control) will be compared on demographic and clinical features, including medical comorbidity, pain, fatigue and post concussive symptoms.
- c. Effectiveness analyses: Random effects models will be used to evaluate the efficacy of the intervention as assessed by HAMD and PHQ9 with comparison of the slopes of the rTMS (Experimental) and sham treatment groups (Control). Random effects models will also be used to compare the two groups over time, controlling for baseline variables found to be statistically significant between the two groups, and the coefficient of interest, such as the interaction between time and treatment assignment. Similar analysis will be done for the CGI-I and BSS scores.

In addition, remission rates (as defined by HAMD score ≤ 7 or PHQ9 = 0) and Improvement rates (as defined by CGI-I scores ≤ 2) between the two groups will be calculated using Fischer's Exact test.

Secondary Objective: To determine the effectiveness of LFR rTMS for the treatment of common co-morbid neuropsychiatric symptoms: (a) Post traumatic stress disorder (PTSD) (b) Sleep disturbance and (c) Cognitive deficits.

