Fatigue: The Fatigue Severity Scale¹¹¹ will be used to assess the severity of fatigue. It has been used both clinically and for research applications, and has been used in the assessment of fatigue in neurological and non-neurological conditions.

Post-Concussive Symptoms: As a myriad of post-concussive symptoms are present after TBI, the Rivermead Postconcussive Questionnaire¹¹² will be used to determine post-concussive symptoms and calculate the total score.

Power Analysis:

The power calculation for this study is based on the study by Fann et al⁴⁵ and our clinical experience. In the open labeled study of sertraline (Zoloft) for the treatment of TBI depression, Fann et al found a response rate (decrease in Hamilton depression scale score of > or = 50%) of 87% and remission rate (Hamilton depression scale score of < or = 7 at the end of treatment) of 67%. Based on these results, we hypothesize improvement in symptoms on the HAMD of 60-70% in the experimental group; and based on our clinical experience, we hypothesize a remission rate of 10% in the Control group. The table (Table 7) below depicts sample sizes for these remission rates with various degrees of power. As this is a pilot study, we have chosen a sample size (N=30) that is feasible and that will allow us to complete the study in the allocated time. Results from this study will help us to develop future studies with larger sample sizes and more conservative numbers. Sample size was calculated with (StataCorp, Texas, 2009) alpha was set at 0.05.

Table 7: Calculation of Sample Size.

Power	Remission rate in Experimental group (control group is 0.1)	N1 (Experimental group)	N2 (control group)	N (total)
0.9	0.7	15	15	30
0.8	0.7	13	13	26
0.75	0.7	12	12	24
0.7	0.7	11	11	22
0.6	0.7	10	10	20
0.9	0.6	21	21	42
0.8	0.6	17	17	34
0.75	0.6	16	16	32
0.7	0.6	15	15	30
0.6	0.6	13	13	26

Safety and tolerability: The following safety measures will be used:

- 1) Collection of vital signs
- 2) Collection of adverse events/side effects. All adverse events including minor rTMS side-effects like post-treatment headache as well as serious and unexpected adverse events like seizure will be recorded. All participants will be encouraged to call or page the PI if they notice any adverse effect or if they are concerned about any medical issues. Side effects will be monitored at each treatment and office visit.

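### Participants withdrawn for suicidality or worsening depression have no required HAMD, PHQ9, BSS or CGI-I rating at or after withdrawal; the main gap is between baseline and the end of session 20

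*Combined protocol and SAP*

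**What the plan says.** Two places in section 4 (Study Procedures) set the withdrawal rule. Under rTMS Treatment & Sham Treatment: "Subjects who become suicidal or develop problems that require aggressive treatment during the course of the study will be withdrawn"; these people then go to the investigator's clinic or are admitted. Under Justification for use of Placebo, if a follow-up visit shows that a participant's "depression is worsening with development of active suicidal thoughts, the participant will be withdrawn from the study for more active treatment". Both describe what happens next as care, and neither mentions study ratings.

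Section 6 (Study Statistics) lists "Primary Efficacy Measures: Changes in HAMD, PHQ9 and BSS". Aim 1(b) is suicidal ideation. The General Description plans plots of outcome scores for "5 visits (baseline, end of 20 LFR rTMS sessions, week 8,12, and 16) by group", and the hypotheses under the primary objective name the same post-baseline times. A weekly form is used during treatment: for the blinding question the technician will "note down the answer in the weekly assessment form", and Data Collection adds "Three TMS forms (adverse effects, Weekly assessment & Operator form) have been uploaded for review". Its other content is not given.

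On missing data, section 6 defines intention-to-treat as everyone randomised, mentions multiple imputation under exploratory work, plans random effects models, and tracks dropouts and compliance. Remission and CGI-I improvement are also compared by Fisher's exact test. Table 7, which sizes the trial, "depicts sample sizes for these remission rates with various degrees of power".

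**The concern.** The event that removes a participant is almost the outcome under study. Someone who becomes actively suicidal in the second week of treatment is a clear failure on BSS and probably on HAMD and PHQ9. Under the visible text that person may have no score after baseline. Someone withdrawn before session 20 has none of the four planned post-baseline scores.

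The planned methods do not close this gap. Intention-to-treat says who belongs in the analysis but creates no ratings. Multiple imputation and random effects models, as ordinarily applied, assume that the recorded data explain why later scores are missing. Here the cause can be a deterioration that was never scored.

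At stake is the Aim 1 comparison, above all Aim 1(b). The effect is understated if the sham arm loses more of its worst scores, about right if losses are equal, and overstated if the active arm loses more.

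**Working it through.** **Inputs from the documents.** 15 per arm; two-sided 0.05; outcome times at baseline, end of session 20, and weeks 8, 12 and 16; hypothesised remission 60–70% active and 10% sham.

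**Inputs assumed.** Withdrawal rates; a true effect of 0.6 SD; a baseline to week-4 correlation of 0.5; and the correlation between the withdrawal trigger and the unrecorded score.

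**1. The plan's own figure.** The two-proportion formula with continuity correction, two-sided 0.05, reproduces all ten rows of Table 7, including 15 per arm for 0.7 v 0.1 at power 0.90 and for 0.6 v 0.1 at power 0.70. Exact power of the planned Fisher test at 15 per arm is 0.894 and 0.739. The sample size is therefore sound on its own inputs. It makes no allowance for participants without a rating.

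**2. Withdrawal before session 20.** Baseline and week-4 scores were simulated as bivariate normal, 1,000,000 per arm. The week-4 score was deleted when a trigger exceeded a cut-off, and the effect was estimated with adjustment for baseline. The trigger also shifts with treatment, so a cut-off that removes 20% of sham removes about 7% of active, and one that removes 10% removes about 3%. The true effect is 0.60.

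| Losses (sham v active) | Correlation 0.5 | Correlation 0.3 | Trigger is the score itself |
|---|---|---|---|
| 20% v 7% | 0.525 | 0.556 | 0.439 |
| 10% v 3% | 0.553 | 0.571 | 0.501 |
| 20% v 20% | 0.60 | 0.60 | 0.60 |
| 7% v 20% | 0.680 | 0.646 | 0.766 |

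At correlations of 0.3 to 0.5 the bias is about 0.03 to 0.08 SD in either direction, and nil with equal losses.

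**3. Bias against precision.** SE = √[(2/15) × (1 − 0.5²)] = √0.10 = 0.316 SD. The 95% half-width is 1.96 × 0.316 = 0.62 SD, or 2.05 × 0.316 = 0.65 SD with a t quantile on 27 degrees of freedom. A bias of 0.03 to 0.08 is about 5% to 13% of that.

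**4. Withdrawal at a follow-up visit.** With five visits, all correlations 0.5, and withdrawal at weeks 8 to 16, the week-16 estimate stays at 0.60 if the triggering visit's rating is kept. If it is lost, the worst case, in which the trigger is the deleted score itself, gives 0.50 (20% sham withdrawal) or 0.54 (10%). At correlations of 0.3 to 0.5 it is about 0.55 to 0.58.

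**5. Fisher tests.** Two-sided p-values when withdrawn non-remitters are left out of the denominator:

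| Case | Active v sham | p |
|---|---|---|
| Near threshold, everyone counted | 8/15 v 2/15 | 0.050 |
| One active left out | 8/14 v 2/15 | 0.021 |
| One, two, three sham left out | 8/15 v 2/14, 2/13, 2/12 | 0.050, 0.055, 0.107 |
| About the plan's rates | 10/15 v 1/15 | 0.0017 |
| Same, three sham left out | 10/15 v 1/12 | 0.0047 |

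The counting rule can move a borderline result across 0.05 when active non-remitters are dropped. It changes nothing at the plan's hypothesised rates.

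**The case against.** The case against has force on several points.

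- **A reader might infer that no rating falls anywhere in weeks 1 to 4.** That is too strong. One is planned at the end of session 20, which is the end of week 4. Moreover, the five-visit list describes plots, the study overview figure is not shown, and the weekly form's content cannot be seen. One can say only that the visible text describes no outcome rating between baseline and the end of session 20.
- **Other records exist.** Side effects are monitored at every treatment and office visit, and the adverse-event questionnaire captures date, severity, action taken and outcome. The event itself may well be logged. That could inform a responder rule, but it is not a BSS or HAMD score.
- **Follow-up visits supply a rating.** Where the visit that reveals the worsening is itself rated, there is little or no bias in this model. The plan does not say that the rating must be completed before withdrawal.
- **The bias is small for a pilot.** This stands. Under plausible correlations it is minor beside the sampling error, and equal losses give none.
- **The Fisher material is selective.** In part this stands. Crossing 0.05 needs a near-threshold table and the loss of active non-remitters; sham losses do not produce it.

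What survives is the silence on ratings at and after withdrawal, and the link between the trigger and the primary measures.

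**Conclusion.** The point holds as a gap in data collection that should be closed. As written, the plan can lose scores from the participants most relevant to Aim 1(b), and its analysis methods cannot recover them. A rating not taken at withdrawal cannot be recreated later.

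Size and direction are unknown, because the documents give no withdrawal rates. On the assumptions above, 0.6 SD becomes 0.52 to 0.57, 0.60, or 0.65 to 0.68, according to which arm loses more. A reader might infer that the trial is biased for or against rTMS, or that its remission result is in doubt. The documents support neither: direction turns on unknown rates, and the remission conclusion is stable at the hypothesised rates. Nor does the point question the clinical decision to withdraw.

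**What to change.** Leave the clinical withdrawal rule as it is, and add the following.

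1. State that withdrawal for clinical need ends study treatment but not outcome collection.
2. Obtain HAMD, PHQ9, BSS and CGI-I at the withdrawal decision, without delaying care, and again at the remaining scheduled visits (end of week 4, weeks 8, 12 and 16) for those who still consent. Use the telephone where needed. The protocol supports this explicitly for PHQ9; for the other scales it rests on the general provision for telephone evaluations under Study Visits.
3. Include all these ratings in the intention-to-treat analysis at their actual dates. Do not carry the withdrawal rating forward to week 4: in the simulation with more sham losses, at correlations of 0.3 to 0.5, that gives 0.66 to 0.70 instead of 0.60.
4. For the remission and CGI-I Fisher tests, name the time point and use recorded status there. Count anyone withdrawn for worsening or suicidality without a rating as not remitted and not improved, and add a sensitivity analysis that leaves them out.

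**Cost.** Protocol and SAP wording, plus one rating at withdrawal and up to four later ratings per withdrawn participant. Later scores include the effect of other treatment, so the estimate is a treatment-policy effect. If other treatment lowers scores by an assumed 0.5 SD, 0.60 becomes 0.54 (20% v 7% withdrawn) or 0.57 (10% v 3%). The non-remitter rule can cost power: at 70% v 10%, with three per arm withdrawn for reasons unrelated to remission, exact power is 0.75, against 0.83 if they are left out and 0.89 with no withdrawals. If those withdrawn would not have remitted anyway, it stays at 0.89.

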Psychiatric Disturbances: The presence or absence of major depression and other psychiatric illness will be determined by administration of the Structured Clinical Interview for DSM IV (SCID-IV⁹⁴). The SCID-IV is designed to identify major Axis I DSM IV diagnoses. It is administered by a clinician and includes an introductory overview followed by nine modules, seven of which represent major Axis-I diagnostic classes. Using a decision tree approach, the SCID guides the clinician in testing diagnostic hypotheses as the interview is conducted. The output of the SCID is a record of the presence or absence of each of the disorders being evaluated, for current episode and for lifetime occurrence. It has been found to be diagnostically accurate and significantly better than the unstructured traditional diagnostic assessments⁹⁵. The major mental Illness variable will be the presence or absence of any major mental illness (e.g., presence/absence of major depression, presence/absence of PTSD).

Depression: The severity of major depression will be assessed by the Hamilton Depression rating scale (HAM-D). This is a 17-item scale that evaluates depressed mood, vegetative and cognitive symptoms of depression. Its validity has been demonstrated in a number of studies and its inter-rater reliability has been consistently high across a number of studies⁹⁶. The depression variable will be the total score on the HAM-D with higher scores indicating the presence of more depressive symptomatology. Severity of depression will also be assessed using a second scale the Patient Health Questionnaire 9 (PHQ9). The PHQ9 is brief, and can be completed by the patient and used over the telephone.

Suicide: Beck Scale for Suicide Ideation (BSS): BSS is a clinician rating scale administered as a semi-structured interview that measures severity, pervasiveness, and characteristics of suicidal thoughts and plans in adults. The total score ranges from 0 to 38, with higher scores indicating more intense levels of suicidal ideation. The internal consistency, concurrent validity, test-retest reliability and predictive validity has been established⁹⁷.

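### Three or four primary scales are each tested at 0.05 in two analysis sets with no deciding result named, and the planned slope comparison is not the end-of-treatment difference that the hypotheses claim

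*Combined protocol and SAP*

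**What the plan says.** **Which scales.** Under Primary Efficacy Measures, section 6 gives "Primary Efficacy Measures: Changes in HAMD, PHQ9 and BSS". The Primary objective assesses depression by HAMD, "Patient Health Questionnaire 9 (PHQ9) and the Clinical Global Impression-Improvement (CGI-I) scale", and suicidal ideation by BSS, which makes four.

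**Hints of an order.** In the variable descriptions, "The depression variable will be the total score on the HAM-D", and "Severity of depression will also be assessed using a second scale the Patient Health Questionnaire 9 (PHQ9"). Hypothesis (a) predicts "statistically significantly lower HAMD PHQ 9 scores (improvement in depression) and higher CGI-I scores (global improvement"); BSS has its own hypothesis (b). None of this is written as a testing order or a success rule.

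**When.** Both hypotheses apply "at the end of the active treatment period (i.e., after 20 sessions) and during the follow-up period (i.e., week 8, 12, and 16 follow-up").

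**Level and analysis sets.** General Description item d: "All statistical tests will be judged for significance based upon a two-sided p-value of less than 0.05". Item a: "Effect assessment will be included in both the ITT and PP dataset". Neither set is named as leading.

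**Model.** Statistical Analysis item c compares the slopes of the two arms in a random effects model. A second random effects model compares the arms over time and offers the time-by-treatment interaction only as an example of the coefficient of interest. Its covariates are those that differ significantly between the arms at baseline. The paragraph on Other Scales says instead that four named confounders (postconcussive symptoms, fatigue, pain and medical comorbidity) will be controlled. Neither place mentions time since injury, on which randomisation is stratified (section 4, Study Design). The Abstract refers to comparisons at each visit as well as over time, without naming a test.

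**Sample size.** Table 7 concerns remission. Item c adds remission as a further Fisher's exact test (HAMD of 7 or less, or PHQ9 of 0, with no time point). Remission is not in the primary measures list.

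**The concern.** With two lists of primary scales, two analysis sets, several time points and more than one model, the same data could be called positive or negative according to the reading adopted once results are known. In a pilot that reported only estimates and intervals this would matter little. Here the hypotheses are framed as statistical significance. The Abstract (Relevance) and the Benefits text in section 7 also say that a finding of efficacy could pass into clinical practice, so a reader needs to know which result would count as that finding.

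A second problem is the mismatch between claim and model. A difference in slope over 16 weeks answers a different question from a difference after 20 sessions. An effect present at the end of treatment that then wanes can leave little or no slope.

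**Working it through.** **1. The plan's own figure.** Inputs from Power Analysis: control remission 0.1, experimental 0.7 or 0.6, alpha 0.05 (taken as two-sided). The two-proportion formula is
n0 = [1.960·√(2p̄(1−p̄)) + z_power·√(p1(1−p1)+p2(1−p2))]² / (p1−p2)²,
with continuity correction n = (n0/4)·[1+√(1+4/(n0·(p1−p2)))]².
For 0.7 against 0.1 at 90% power, p̄ = 0.4, n0 = (1.358+0.702)²/0.36 = 11.79 and n = 14.93, rounded up to 15. All ten rows match: 15, 13, 12, 11, 10 and 21, 17, 16, 15, 13 per arm. Exact Fisher power at 15 per arm is 0.89 (0.7 against 0.1) and 0.74 (0.6 against 0.1).

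**2. Does a remission-based size leave HAMD short?** Assume remission by HAMD alone and normal scores with equal SD. The planned rates then imply differences of z(0.7)−z(0.1) = 1.81 SD and z(0.6)−z(0.1) = 1.53 SD. A t-test with 15 per arm has 99.8% and 98% power at those differences. No shortfall is shown.

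**3. Slope against end of treatment.** Visits are at weeks 0, 4, 8, 12 and 16, with mean 8 and Σ(t−8)² = 64+16+0+16+64 = 160. With complete data and linear time, the slope difference is Σ(t−8)·d_t/160, where d_t is the benefit at week t. Take d = 0 at baseline and 1 at week 4; the later course is assumed.

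| Benefit at weeks 4, 8, 12, 16 | Calculation | Slope per week |
|---|---|---|
| 1, 1, 1, 1 | (−4+0+4+8)/160 | 0.050 |
| 1, 0.83, 0.67, 0.5 | (−4+0+2.67+4)/160 | 0.017 |
| 1, 0.75, 0.5, 0.25 | (−4+0+2+2)/160 | 0 |

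In the last row, a 1 SD benefit at week 4 has a 2.5% chance of a significant favourable slope. A test of change to week 4 has 64 to 94% power (assumed correlation between visits 0.3 to 0.7).

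**4. False-positive chance by reading.** Two-sided t-tests at 0.05, 15 per arm, no true effect, one analysis set, simulated with the same correlation between every pair of scales (0.3 to 0.8; the documents give none).

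| What counts as success | Chance of a false positive |
|---|---|
| HAMD, PHQ9 and CGI-I together, or BSS | 5.0–5.3% |
| HAMD or BSS | 8–10% |
| Any of three scales | 10–14% |
| Any of four scales | 12–17% |

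Independent tests would give 1−0.95³ = 14.3% and 1−0.95⁴ = 18.5% for the last two rows. About half of each any-scale figure is a false finding of harm. Counting only results that favour rTMS, any of three gives about 5–7% and any of four about 6–9%, against a nominal 2.5%.

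**5. Precision for one scale score.** With 15 per arm, an unadjusted t-test detects 1.06 SD at 80% power and 1.23 SD at 90%. The 95% CI half-width is 2.048·√(2/15) = 0.75 SD.

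**The case against.** **The literal wording controls error.** Hypothesis (a) joins its scales with a conjunction, and the reading that follows it most closely gives 5.0–5.3%. This stands. A reader might infer from the 10–17% figures that the plan has that error rate, but no section says that one significant scale, or a hit in either ITT or PP, is enough. Reporting PP beside ITT is ordinary practice. What remains is that the plan commits to no reading.

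**The plan can already test week 4.** A reader might infer that no planned analysis addresses end of treatment. That goes too far. Linear time is never stated, the second model would give the week-4 contrast if visit were a category, and the Abstract mentions visit-by-visit comparison. But no section specifies that coding or names that contrast as the test.

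**The trial is underpowered for its primary scales.** This may be inferred from Table 7, but the documents do not support it: the table is correct and step 2 shows no shortfall. The fault is a mismatch of outcome.

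**Covariates are purely data-driven.** Not quite. Other Scales names four in advance. The defect is that the two passages conflict.

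**It is a pilot.** Power Analysis and Benefits both say that the results will inform larger studies. That lowers the stakes and supports keeping N=30, but it does not say which of the planned significance tests decides.

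**Conclusion.** The point holds as a cheap improvement. Three facts rest on the text alone: the lists of primary scales differ, no scale, time point or analysis set is named as deciding, and a slope comparison is not the end-of-treatment difference that the hypotheses state. The size of the ambiguity, from about 5% to 17% depending on the reading, rests on assumed correlations of 0.3 to 0.8 and counts both directions. It measures what is left open, not an error rate of the plan. The loss of signal in the slope, from 0.050 to 0 per week, rests on linear time and assumed fading profiles; an effect that holds or builds would still show. The covariate conflict is real. Table 7 needs a label, not a new calculation.

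**What to change.** Keep N=30 and the pilot framing.

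- **Deciding test for Aim 1a.** Use the ITT treatment contrast on HAMD at the end of treatment. Take it from the planned random effects model fitted to the post-baseline visits, with visit as a category, adjusted for baseline HAMD and the time-since-injury stratum, with a small-sample t reference.
- **Covariates.** Drop selection by baseline significance. Move the four covariates under Other Scales to a prespecified sensitivity analysis.
- **Aim 1b.** Keep BSS as its own test at the same time point in ITT. Either state that error is controlled separately for each hypothesis, or prespecify an order. Testing BSS only after HAMD succeeds is one option with a cost to Aim 1b, not a correction.
- **Secondary.** Report slopes, later visits, PHQ9, CGI-I, remission and PP with estimates and 95% CIs.
- **Consistency.** Make the two lists of primary measures agree. Correct the CGI-I direction: the hypothesis treats a higher score as improvement, while the scale description makes 7 very much worse.
- **Remission and Table 7.** Label the table as remission only. Give the Fisher test one definition and one time point. The definition quoted in Power Analysis (HAMD of 7 or less at end of treatment) belongs to the cited open-label sertraline study and should be adopted explicitly if it is intended.
- **Precision.** Add the step 5 figures, marked as rough for BSS, since suicidal ideation is not an entry requirement and the score may be skewed.

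**Cost.** Protocol and analysis text only, with no added patients, visits or procedures. The price is in what can be claimed: a benefit seen only after week 4, only on another scale or only in PP would no longer be a primary success for depression.
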